## **Title of Project**

Coronavirus disease 2019 (COVID-19) during pregnancy: prevalence of seroconversion, effect on maternal and perinatal outcomes and risk of vertical transmission

Keywords: 1) COVID-19; 2) pregnancy; 3) vertical transmission; 4) pregnancy loss; 5) ACE2 TMPRSS2

## **Project objectives**

- 1) To determine the rate of SARS-CoV-2 seroconversion in unselected pregnant women in Hong Kong.
- 2) To determine the rate of SARS-CoV-2 infection in women presenting with miscarriage and stillbirth.
- 3) To follow the pregnancy course and perinatal outcome of confirmed COVID-19-infected pregnant cases.
- 4) To determine the risk and characteristics of vertical transmission.
- 5) To evaluate the placental barrier, immune response and fetal damage in vertical transmission of SARS-CoV-2.

### **• Background of research and expected project commencement date**

Emerging infections have been shown to have an important impact on pregnant women and their fetuses. Recent examples include the 2009 pandemic H1N1 influenza virus and the Zika virus. The emergence of a novel coronavirus not previously seen in humans, namely severe acute respiratory syndrome coronavirus 2 (SARS-CoV-2), was first reported in Wuhan, China, on December 31, 2019. The coronavirus disease 2019 (COVID-19), caused by the SARS-CoV-2, was declared by the World Health Organization (WHO) a pandemic on 11 March 2020. Since then, the number of reported cases has increased rapidly, with more than 10 million cases and 500000 deaths as of 1 July, 2020.

Coronaviruses are single-stranded RNA, non-segmented, enveloped viruses, which cause illness ranging in severity from a common cold to severe and fatal illness. The term coronavirus derives from the Latin word corona, which means crown or halo; the designation arises from the appearance of coronavirus virions viewed by electron microscopy (EM), in which the virus particles display a crown-like fringe typically referred to as spikes. In the past 2 decades, two notable coronaviruses, severe acute respiratory syndrome coronavirus (SARS-CoV) and the Middle East respiratory syndrome coronavirus (MERS-CoV), have caused severe respiratory illness in humans. Within a short period of time, the third coronavirus, SARS-CoV-2, has infected far more people than were reported for MERS-CoV and SARS-CoV combined.

It is recognized that pregnant women are at an increased risk of acquiring viral respiratory infection and developing severe pneumonia due to the physiologic changes in their immune and cardiopulmonary systems. It is important to determine the effect of the SARS-CoV-2 infection

and its disease (COVID-19) on pregnant women and their fetuses as careful risk-benefit analysis and decisions regarding treatment and interventions during pregnancy are crucial. It is critical to acquire high-quality data on maternal and perinatal outcomes and risk of vertical transmission. The first study describing the clinical characteristics and investigating the possibility of vertical transmission of SARS-CoV-2 in 9 pregnant women with laboratory-confirmed COVID-19, demonstrated that the severity of COVID-19 in pregnant women was similar to that in non-pregnant adults and that there was no evidence of vertical transmission when the infection manifests during the third trimester of pregnancy as SARS-CoV-2 was not detected in amniotic fluid, cord blood and neonatal throat swab samples in six cases. However, there remain many unanswered questions concerning mother-to-child-transmission of SARS-CoV-2.

Several studies have attempted to determine the potential risk of vertical transmission, however, relevant biological samples have not been collected in a systematic manner. Paired maternal-perinatal testing i.e. with vaginal, cervical or rectal swabs, has been performed to detect genital tract viral shedding during vaginal delivery in 22.5% of the case-series. Breast milk has also been tested for SARS-CoV-2 using reverse transcription polymerase chain reaction (RT-PCR) in 22.5% of the studies. Five studies have reported immunoglobulin (Ig)G and IgM serology in the mothers and the neonates with additional cytokine assays. Several studies have evaluated the placenta for infectious pathology. Twenty-five percent of these reports have documented neonatal SARS-CoV-2 infection. Reports from Italy, Peru and Iran attributed neonatal infection to horizontal transmission from RT-PCR positive mothers via breastfeeding without masks (respiratory droplets) and vaginal delivery (exposure to genital secretions).

Two reports suggested possible transplacental infection due to the presence of neonatal IgM antibodies and abnormal cytokine levels after birth, since IgM is not transmitted transplacentally and may have been produced by the fetus in response to in utero exposure to SARS-CoV-2. In both reports, RT-PCR of neonatal nasopharyngeal swab and maternal vaginal secretions were negative. Specifically, in the study of Dong et al., the observed decline of anti-SARS-CoV-2 IgG and IgM levels from 140.32 AU/mL (normal range is 0–10 AU/mL) and 45.83 AU/mL (normal range is 0–10 AU/mL), respectively, at 2 hours after birth to 69.94 AU/mL and 11.75 AU/mL, respectively, at 14 days of age, is not consistent with the typical profile of the body's antibody response to acute viral infection. The rapid decline of anti-SARS-CoV-2 IgG antibody level in the infant within 14 days, in addition to the decline in IgM antibody level, strongly indicates that the neonatal anti-SARS-CoV-2 IgG antibodies were derived transplacentally from the mother and their production was not actively induced by the presumed neonatal infection.

Nevertheless, there are several limitations in addressing the issue of vertical transmission as most studies reported infections in the third trimester where the interval between infection and delivery is relatively short. The risks of transplacental infection in the first and second trimesters, with a potentially longer fetal exposure time, are unclear. While most reported cases have been delivered by Cesarean section, the evidence does not suggest a clear association between neonatal SARS-CoV-2 and vaginal delivery.

With regard to whether SARS-CoV-2 infection or its disease is associated with pregnancy loss,

existing evidence is unclear. Limited data on SARS-CoV (2003) reported a high first trimester miscarriage risk of 50%. A recent high-quality systematic review evaluating the effect of COVID-19 on perinatal outcomes reported that there were only four reported cases of miscarriage among 295 pregnancies affected by COVID-19, suggesting that the miscarriage risk is not significantly increased by COVID-19. However, it is likely that cases of miscarriage associated with COVID-19 have been missed or underreported because pregnancy symptoms can mask COVID-19 symptoms, such as myalgia and fatigue. There was a case report of second trimester miscarriage associated with SARS-CoV-2 infection, where the virus was isolated in the placenta but not in the abortus. This case raised the possibility of placental infection with SARS-CoV-2. Though there was no evidence of vertical transmission, absence of the virus in the abortus was not surprising given the short interval between maternal infection and miscarriage. Whether SARS-CoV-2 crosses the placental barrier warrants further investigation. In a non-consecutive case series of 9 cases of severe COVID-19 there were two pregnant women with intrauterine fetal death. Further, latest evidence has demonstrated that placentas from pregnant women affected by COVID-19 show patterns of placental injury reflecting abnormalities in oxygenation within the intervillous space associated with adverse perinatal outcomes, such as stillbirth, fetal growth restriction (FGR). Based on data from the SARS-CoV (2003) case-series, 80% patients who presented after 24 weeks had preterm birth and 2 mothers recovered without delivery, but their ongoing pregnancies were complicated by FGR. It is important to determine if SARS-CoV-2 infection increases the risk of pregnancy loss, preterm birth, FGR or other pregnancy complications.

Emerging evidence suggests that a significant proportion of SARS-CoV-2 carriers are asymptomatic. This poses significant challenges in regard to the management of pregnancy and childbirth during the COVID-19 pandemic. Pregnancy symptoms can mask COVID-19 symptoms, especially if they are mild. Using the approach of targeted testing based on a significant epidemiological history or symptoms, a cohort study of 116 pregnant women with COVID-19 in China demonstrated that 23.3% of cases were asymptomatic. Using the approach of universal testing by RT-PCR in women admitted for delivery, the rates of positive SARS-CoV-2 result in asymptomatic women were 13.5% and 2.9% in and outside highly endemic regions in the United States, respectively, and 3.8% in Tokyo, Japan.

In this proposal, we plan to perform a systematic assessment of seroconversion, maternal and perinatal outcome and risk of vertical transmission of SARS-CoV-2 infection during pregnancy.

- **Research plan and methodology**

The research project will engage in collaborative research across obstetricians/maternal-fetal medicine (MFM) subspecialists (**[name], [name], [name], [name], [name]**), gynecologist (**[name]**), infectious disease specialists (**[name], [name]**), pediatrician (**[name]**), developmental and molecular biologists (**[name], [name]**) and biostatistician/bioinformatician (**[name]**) between the **CUHK, China and Spain**.

**Objective 1: Seroconversion during pregnancy**

**Methodology:** a longitudinal study. Inclusion criteria: (1) pregnant women who attended for Down syndrome screening (DSS) at 11-13 weeks and had a serum sample (**A**) taken between 1 November 2019 and 1 June 2020; (2) consented for stored serum for future research; and (3) intended to deliver at the booking hospital. Ethics approval at Prince of Wales Hospital (PWH) has been acquired (CREC Ref 2020.214). A list of eligible patients has been identified from our DSS database. We have started recruiting eligible patients through telephone call. An alert is set within the Hospital Authority Clinical Management System and therefore when the participant attends for delivery, we will confirm informed consent and collect the second serum sample (**B**), which will be stored at -80°C for subsequent testing. Ethics approval at Kwong Wah Hospital (KWH) has been submitted. The research team believes that it is critical to utilize stored serum samples from women who attended for routine DSS between November 2019 and June 2020 as this will capture the seroconversion data from the start of the outbreak until after the peak of the outbreak. Assuming a worst-case scenario of SARS-CoV-2 penetrance of 1% we estimate that **2400 women** will need to be recruited from amongst the 4800 women who attended for DSS during the study period. For all consented participants, **paired blood samples A and B** will be analyzed for anti-SARS-CoV-2 specific antibodies (Elecsys Anti-SARS-CoV-2, cobas e411 analyzer, Roche Diagnostics GmbH, Mannheim, Germany). Results on the rate of seroconversion will be summarized in counts and percentages. **Target achievement:** we aim to recruit 2400 unselected pregnant women to quantify the rate of seroconversion of SARS-CoV-2 during pregnancy from the start until after the peak of the COVID-19 outbreak in Hong Kong. This will allow us to determine the rate of women of childbearing age who have potentially been infected with SARS-CoV-2, but have remained asymptomatic or mildly symptomatic and undetected.

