### **Objective 3: Pregnancy course and perinatal outcome**

Methodology: a longitudinal study. For pregnant women affected by COVID-19, following recovery, 4-weekly ultrasound scan for assessing fetal size, amniotic fluid volume, fetal Dopplers (umbilical artery, middle cerebral artery, ductus venosus), uterine artery Doppler and placental morphology (echogenicity, thickness, appearance) and function will be done. For first and early second trimester infected cases, a detailed fetal morphological scan will be undertaken to determine the risk of structural malformation. The following information will be collected: (i) maternal demographics including: age, weight, height, racial origin, smoking, medical history of chronic hypertension, cardiovascular disease, diabetes mellitus and respiratory disease, drug history, method of conception, parity, past obstetric history; (ii) delivery outcome: gestational age at delivery, mode of delivery, complications including stillbirth, FGR, preterm birth, preeclampsia; (iii) neonatal data: birthweight, sex, Apgar scores, cord arterial and venous pH and base excess, neonatal outcome, admission to neonatal intensive care unit (NICU), complications such as sepsis, anemia, intraventricular hemorrhage, necrotizing enterocolitis, respiratory distress syndrome, need for respiratory support, laboratory findings; (iv) COVID-19 specific data: gestational age at clinical manifestation; symptoms and signs; epidemiological history; laboratory and radiological findings; treatment measures; COVID-19 severity and outcomes; and intervals from onset of disease to hospital admission, delivery and recovery will be recorded. Results on maternal and perinatal outcomes will be summarized in counts and percentages and median and ranges. Target achievement: To date, there are 5 reported pregnant cases affected by COVID-19 in Hong Kong. We anticipate that between Hong Kong, China and Spain, we will recruit 40-50 pregnancies affected by COVID-19 with complete data according to protocol. We will learn a complete picture of the pregnancy course and perinatal outcome of cases affected by COVID-19. Such data will form the basis of counselling regarding the impact of coronavirus on pregnancy and perinatal outcome.

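### Objective 1 plans only a seroconversion rate between samples A and B, but presents it as the rate of women infected and undetected, which is a different quantity

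*Protocol*

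**What the plan says.** In the Protocol's Project objectives, the first aim is "To determine the rate of SARS-CoV-2 seroconversion in unselected pregnant women in Hong Kong". The section Objective 1: Seroconversion during pregnancy describes a longitudinal study. Sample A is the stored serum from Down syndrome screening at 11-13 weeks, "taken between 1 November 2019 and 1 June 2020"; sample B is taken at delivery. For every consented participant both sera "will be analyzed for anti-SARS-CoV-2 specific antibodies".

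The result is fixed in one sentence: "Results on the rate of seroconversion will be summarized in counts and percentages". The target statement at the end of the section then draws the conclusion: "This will allow us to determine the rate of women of childbearing age who have potentially been infected with SARS-CoV-2, but have remained asymptomatic", continuing to mildly symptomatic and undetected women.

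The three inclusion criteria are attendance for screening with a serum sample in the window, consent to stored serum, and intention to deliver at the booking hospital. None concerns a previous COVID-19 diagnosis. The section names no symptom or prior-test data. COVID-19-specific data are listed only under Objective 3, for women known to be affected.

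**The concern.** With paired samples, seroconversion ordinarily means negative at A and positive at B. That measures new infection between 11-13 weeks and delivery. The target sentence claims something else: how many women were infected and never detected. The two differ in two ways.

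- **Infection before A.** The protocol justifies the A window by saying that it runs from the start of the outbreak until after its peak. Some A samples will therefore follow exposure. A woman who is antibody-positive at A adds nothing to the seroconversion rate, although she has been infected. This lowers the figure.
- **Diagnosed infection.** A woman diagnosed between A and B counts as a seroconversion, although she was detected. Objective 3 states: "To date, there are 5 reported pregnant cases affected by COVID-19 in Hong Kong". Including such women raises the figure relative to the undetected rate.

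The target sentence is the headline conclusion of Objective 1. A reader given only the planned percentage could not tell how far it lies from the claimed quantity, or on which side.

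**Working it through.** **Inputs from the protocol.** A window 1 November 2019 to 1 June 2020; B at delivery; 2400 women; assumed penetrance 1%; five known affected pregnant women in Hong Kong (Objective 3, Study coordination). The Background section says the virus "was first reported in Wuhan, China, on December 31, 2019" and dates the pandemic declaration to 11 March 2020.

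**The plan's own figure.** 2400 × 0.01 = 24 infected women; exact 95% CI for 24/2400 is 0.64-1.48%. The protocol states no precision target for 2400. A 95% half-width of 0.4 points would need 1.96² × 0.01 × 0.99 / 0.004² = 2377, which is close. The point does not depend on how 2400 was chosen.

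**Can women be positive at A?** The window has 214 days, of which 154 (72%) fall on or after 31 December 2019. That date is the first report in Wuhan, not the start in Hong Kong, so 72% shows only that early exposure is possible. It does not measure its share.

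**Share of infections before A (assumed epidemic shapes).** A dates are spread evenly, B = A + 28 weeks, and the antibody lag is 0 or 14 days. For each A date:
- missed = days from epidemic start to (A − lag);
- total = days from epidemic start to (B − lag);
- both are capped at the epidemic end where one is set;
- share = sum of missed / sum of total.

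| Assumed incidence | Lag 0 | Lag 14 days |
|---|---|---|
| Flat, 31 Dec 2019 to delivery | 0.227 | 0.199 |
| Flat, 31 Dec 2019 to 1 June 2020 | 0.362 | 0.302 |
| Flat, 31 Jan 2020 to delivery | 0.166 | 0.139 |
| Flat, 29 Feb 2020 to delivery | 0.112 | 0.088 |
| Flat, 11 Mar 2020 to delivery | 0.093 | 0.070 |
| 4-week wave centred 1 Feb 2020 | 0.568 | 0.502 |
| 4-week wave centred 1 Mar 2020 | 0.432 | 0.367 |
| 4-week wave centred 31 Mar 2020 | 0.292 | 0.227 |
| 4-week wave centred 1 May 2020 | 0.147 | 0.083 |
| 4-week wave centred 1 July 2020 | 0 | 0 |

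**Effect on the ever-infected rate.** At 24 infections, the flat scenarios report between 24 × (1 − 0.362) = 15.3 women (0.64%) and 24 × (1 − 0.070) = 22.3 women (0.93%), leaving out about 2 to 9. At its extreme this reaches the lower limit of the sampling interval; otherwise it lies inside it. The earliest wave would leave 24 × (1 − 0.568) = 10.4 women (0.43%), below that interval.

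**Effect on the undetected rate.** Suppose 5 of the 24 had been diagnosed, so that 24 − 5 = 19 were undetected (0.79%). Suppose also that all 5 seroconverted between A and B and that the A-positive women are among the other 19. Then the ratio of reported to undetected is:
- 15.3 / 19 = 0.81 (19% too low);
- 22.3 / 19 = 1.17 (17% too high);
- 24 / 19 = 1.26 if nobody was positive at A.

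The sign depends on two quantities that the planned result does not show.

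**The case against.** The protocol never says that women positive at A are excluded. That follows from the strict meaning of seroconversion, which the section does not define. The project title speaks of the prevalence of seroconversion, and Objective 1 links the term to penetrance, so a looser meaning of any positive result is conceivable. On that reading the first gap closes. The second does not, because diagnosed women would still be counted, and the paired longitudinal design makes the strict reading the natural one.

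Detailed table specifications can be left to a statistical analysis plan. That is true, but the protocol itself fixes both the summary and the conclusion drawn from it, and the fault lies in that pairing. The word potentially softens the claim about infection, but not the claim that the infections went undetected.

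Nothing shows that any of the five known women attended screening at a study hospital in the window. The investigators follow affected women under Objective 3 and could recognise an overlap. This stands: the figure of five is an illustration, not an estimate. Objective 4 cites a Table 3 that is not in the text at hand, so a separation described there cannot be excluded.

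Finally, most of the flat-incidence shift is within sampling error. That also stands, but the shift is systematic, and a confidence interval around the seroconversion rate would not reflect it.

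**Conclusion.** The concern holds and should be fixed. The A-to-B rate is a valid answer to the first aim as listed under Project objectives. It does not support the sentence on infected and undetected women that closes Objective 1. The mismatch follows from the protocol's wording and needs no assumption beyond the ordinary meaning of seroconversion.

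The size does rest on assumptions. Infections before A make up 7-36% of the total under the flat scenarios and 0-57% under single waves. If few women were infected before 11-13 weeks and none of the participants was diagnosed, the practical effect is small. The net direction for undetected infection cannot be determined from the document.

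**What to change.** Define seroconversion as negative at A and positive at B, and report from the assays already planned:

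1. positivity at A, by calendar month of sampling;
2. A-negative and B-positive women, with A-negative women as the denominator;
3. women positive at A or B, over all pairs.

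Use the third figure for the statement about potential infection. For the statement about undetected infection, check the records of each woman who tests positive and count those with a prior COVID-19 diagnosis separately. If that is not wanted, limit the target sentence to new infection between 11-13 weeks and delivery.

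The cost is a change of protocol wording and, if the undetected claim is kept, one record check per positive woman, about 24 at the plan's 1%. No further samples or assays are needed.

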### **Objective 2: SARS-CoV-2 and pregnancy loss**

**Methodology:** a cross-sectional study. We plan to recruit pregnant women presenting with first and second trimester miscarriage in Hong Kong and Spain, as well as those with stillbirth during periods of 6 and 12 months, respectively. The overall rates of clinical first trimester miscarriage, second trimester miscarriage and stillbirth are approximately 10%, 1% and 0.1-0.3%, respectively. We plan to recruit first trimester miscarriage cases undergoing surgical management in order to minimize the risk of contamination. Regarding second trimester miscarriage, a mixture of spontaneous, medical and surgical management cases will be recruited as the latter is not frequently performed due to the recognized increased risk of uterine perforation and cervical laceration. For cases of miscarriage, we anticipate a 50% uptake and accounting for women seeking private care (70%), we aim to recruit approximately **500 cases**. Regarding stillbirth, during a 1-year period we anticipate a 50% uptake and aim to recruit 5 cases. Biological samples to be collected and tested are listed in Table 1. For first trimester products of conception (POC), specimen will be washed in cold saline or PBS to remove blood, which will then be dissected into small pieces and stored in micro-tubes that will be frozen by snap freezing in liquid nitrogen or dry ice and subsequently stored at -80°C. For second trimester POC and stillborn baby, placenta will be washed in cold saline or PBS to remove blood. Dissect the placenta into 5 full-thickness samples (1 x 1 cm) from 5 random sampling sites, away from cord insertion site and as far apart from each other as possible. One of these samples will be stored in 10% buffer-formalin and another 1 of them will be stored in EM fixative. For the remaining 3 samples, they will be dissected into 3 parts: chorionic plate, villous and maternal decidua; and store these samples into

separate micro-tubes that will be frozen by snap freezing in liquid nitrogen or dry ice and subsequently stored at -80°C. Abortus/stillborn baby will be washed in cold saline or PBS to remove blood. Dissect the abortus/stillborn baby into different body parts, e.g. lungs, cartilage, skull, brain, muscle, intestines, and store them into separate micro-tubes that will be frozen by snap freezing in liquid nitrogen or dry ice and subsequently stored at -80°C. Stillborn baby will also undergo routine autopsy and histopathological examination (HPE) of placenta. All placentas will be photographed against a scale bar. In addition, hematoxylin-eosin, myeloperoxidase immunohistochemistry, Gram, and periodic acid-Schiff colorations will be performed on POC and placenta that are tested positive for SARS-CoV-2 to exclude coexisting bacterial infection. Results on the rate of SARS-CoV-2 infection in women with pregnancy loss will be summarized in counts and percentages. Target achievement: we aim to recruit 500 and 5 pregnant women with miscarriage and stillbirth, respectively, to determine the rate of SARS-CoV-2 infection in women presenting with early and late pregnancy loss, and in cases with positive SARS-CoV-2, matched with negative cases, whether vertical transmission has contributed to these complications (see details in objective 5).

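### Do Objective 2's targets of 500 miscarriages and 5 stillbirths contradict the rates and windows given for them?

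*Protocol*

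**What the plan says.** All the inputs stand in the protocol, section Objective 2: SARS-CoV-2 and pregnancy loss.

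- **Who and when.** Recruitment covers "first and second trimester miscarriage in Hong Kong and Spain, as well as those with stillbirth during periods of 6 and 12 months", respectively. The 12 months belong to stillbirth, as a later sentence confirms: "Regarding stillbirth, during a 1-year period we anticipate a 50% uptake and aim to recruit 5 cases".
- **Rates.** "The overall rates of clinical first trimester miscarriage, second trimester miscarriage and stillbirth are approximately 10%, 1% and 0.1-0.3%, respectively".
- **Uptake and private care.** "For cases of miscarriage, we anticipate a 50% uptake and accounting for women seeking private care (70%), we aim to recruit approximately" 500 cases. No private-care allowance is given for stillbirth.
- **Restriction.** "We plan to recruit first trimester miscarriage cases undergoing surgical management in order to minimize the risk of contamination". Second trimester cases may be managed in any way.
- **Targets repeated.** The target statement closing the section reads "we aim to recruit 500 and 5 pregnant women with miscarriage and stillbirth, respectively".

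The section gives no number of pregnancies or births for either outcome. Rates of infection are to be reported as counts and percentages.

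**The concern.** The section lists rates, windows, uptake and a private-care allowance, and then gives 500 and 5. A reader naturally takes the two targets as products of those inputs. Neither can be rebuilt alone, because the number of pregnancies is missing. On a shared catchment, however, that number cancels from the ratio of the two, and the ratio can be tested. It comes out well below the 100 that 500 and 5 imply.

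If one target were wrong, the planned precision for the infection rate in early or late loss would be misjudged. Infected losses also supply tissue for Objective 5, so recruitment planning there would be affected too.

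**Working it through.** **Inputs (all from Objective 2).** Miscarriage rate 0.10 + 0.01 = 0.11; stillbirth rate r = 0.001 to 0.003; windows 0.5 and 1 year; uptake 0.5 for each. Let f be the fraction of miscarriages kept after private care, relative to the fraction of stillbirths kept, and N the pregnancies per year in a shared catchment.

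**Formula.** Recruits = N × rate × years × uptake × fraction kept. Then

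miscarriages per stillbirth = (0.11 × 0.5 × 0.5 × f) / (r × 1 × 0.5) = 0.055 f / r.

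**Plan's own ratio.** 500 / 5 = 100.

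**Ratio on one shared catchment**

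| Reading | r = 0.1% | r = 0.3% |
|---|---|---|
| No private-care loss, or an equal loss (f = 1) | 55.0 | 18.3 |
| Same, stillbirth per birth (divide by 1 − 0.11 = 0.89) | 61.8 | 20.6 |
| 70% kept, miscarriage only (f = 0.7) | 38.5 | 12.8 |
| 30% kept, miscarriage only (f = 0.3) | 16.5 | 5.5 |
| Second trimester cases over 12 months: (0.05 + 0.01) / r | 60.0 | 20.0 |
| All miscarriages over 12 months: 0.11 / r | 110.0 | 36.7 |

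Only the last row reaches 100, and it contradicts the stated 6 months. Rounding does not close the gap: 450 / 5.5 = 81.8. A ratio of 100 with f = 1 would need r = 0.055 / 100 = 0.055%, below the stated range.

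**What each target implies for the other (f = 1, shared catchment)**

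- 5 stillbirths need N = 5 / (0.5 r) = 10,000 (0.1%) or 3,333 (0.3%). These give N × 0.11 × 0.5 × 0.5 = 275 or 92 miscarriages.
- 500 miscarriages need N = 500 / 0.0275 = 18,182. This gives 18,182 × r × 0.5 = 9.1 to 27.3 stillbirths.

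**What reconciles them.** Drop the shared catchment. With f = 1, the effective stillbirth base must be 0.055 / (100 r) of the miscarriage base: 55% at r = 0.1%, 18% at 0.3%. Fewer sites for stillbirth would do this. So would a heavier private-care or eligibility loss for stillbirth on the same sites: at r = 0.1%, keeping stillbirths at 55% of the miscarriage fraction is enough. If the 70% reduces miscarriage alone, the stillbirth base must be smaller still.

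**Consequence for precision.** The exact 95% upper limit with zero positives is 1 − 0.025^(1/n).

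| Outcome | n | Upper limit |
|---|---|---|
| Miscarriage | 500 | 0.7% |
| Miscarriage | 275 | 1.3% |
| Stillbirth | 5 | 52% |
| Stillbirth | 9 | 34% |
| Stillbirth | 27 | 13% |

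**The case for a change.** The strongest case for a change is that the test uses only the protocol's figures and that generous readings were tried. Counting stillbirth per birth, rounding both targets and lengthening the second trimester window all leave the ratio short of 100. Taking the 70% as written, for miscarriage only, widens the gap. The surgical-only rule can only lower the miscarriage count further. At 10% against 1%, about 0.10 / 0.11 × 500 = 455 of the 500 would be first trimester cases subject to that rule, and no allowance for it is visible. Catchment and targets are protocol matters, and a sentence naming them would cost little.

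The arithmetic stands. So does the observation that the catchment for each outcome and the meaning of the 70% (share lost or share kept) are not spelled out.

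What does not stand is the step from there to an error. It needs one catchment with equal losses, and the visible text does not say so. Hong Kong and Spain are attached to miscarriage; stillbirth is added without a place. The Study coordination section puts collection of products of conception and recruitment of stillbirths under one gynecologist, and mentions Spain for Objective 4 recruitment. That does not prove that stillbirths come from Hong Kong alone, but unequal catchments are at least as natural a reading as a shared one. The surgical share is not given either, so that remark has no size.

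**Conclusion.** The two targets do not follow together from the stated inputs on one catchment with equal losses: 18-55 (at most about 62) against 100, a gap of at least 100 / 61.8 = 1.6-fold. They are compatible if stillbirths have a smaller effective catchment, about 18-55% of that for miscarriage with equal private-care loss. The protocol rules out neither situation, so neither 500 nor 5 is shown to be wrong, and there is no figure to correct.

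This is a gap in exposition that the investigators can fill from their own site volumes. Both numbers are recruitment aims, the larger one explicitly approximate, for a descriptive objective with no hypothesis test. Each rate is computed on the women actually recruited, so a target that is missed or exceeded does not by itself bias it. Precision moves modestly for miscarriage (upper limit 0.7% or 1.3%). For stillbirth it is very poor at 5 cases and still weak at 9; even 27 cases leave an upper limit of 13%. Followed as written, the plan still yields sound counts and percentages, and no change follows.

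### Can about five stillbirths serve Objective 2's aim of determining an infection rate, or should that target or aim be changed?

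*Protocol*

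**What the plan says.** The Project objectives section of the protocol gives the second aim as "To determine the rate of SARS-CoV-2 infection in women presenting with miscarriage and stillbirth". The Objective 2 section describes a cross-sectional study recruiting women with "first and second trimester miscarriage in Hong Kong and Spain, as well as those with stillbirth during periods of 6 and 12 months, respectively". It gives background frequencies: "The overall rates of clinical first trimester miscarriage, second trimester miscarriage and stillbirth are approximately 10%, 1% and 0.1-0.3%, respectively". The stillbirth number then comes from a fixed window and an expected uptake: "Regarding stillbirth, during a 1-year period we anticipate a 50% uptake and aim to recruit 5 cases".

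The target statement at the end of that section says "we aim to recruit 500 and 5 pregnant women with miscarriage and stillbirth, respectively", with the purpose "to determine the rate of SARS-CoV-2 infection in women presenting with early and late pregnancy loss". The only analysis described is "Results on the rate of SARS-CoV-2 infection in women with pregnancy loss will be summarized in counts and percentages". The same statement adds that positive losses, matched with negative ones, go forward to the mechanistic work in Objective 5. No expected infection rate, precision or power is stated for stillbirth, and no comparison of stillbirth with miscarriage is planned.

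**The concern.** The protocol speaks of determining a rate, names stillbirth explicitly and gives it its own number, and that number is five. With five women the smallest non-zero estimate is 20%. That is above every infection rate the protocol quotes for pregnant women: the pessimistic 1% assumed in Objective 1, and from the Background section "the rates of positive SARS-CoV-2 result in asymptomatic women were 13.5% and 2.9% in and outside highly endemic regions in the United States", plus 3.8% in Tokyo.

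Two outcomes cause worry. Zero positives, the likeliest result at 1 to 3.8%, would rule out very little. One positive would print as 20% beside a well-estimated miscarriage rate, and a reader might take one woman's result for a stillbirth effect. The two targets also seem to imply catchments of different size, which suggests that more stillbirths might have been available. If so, the aim would be out of reach for a reason that recruitment could cure.

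**Working it through.** **Where the 5 comes from.** Inputs from the Objective 2 section: stillbirth rate 0.1 to 0.3%, uptake 50%, one year. The formula is recruited cases = births per year × rate × uptake. The protocol gives no number of births, so 5 cannot be reproduced directly. Solving backwards:

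- 5 / 0.5 / 0.003 = 3,333 births a year
- 5 / 0.5 / 0.001 = 10,000 births a year

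As a plausibility check, assume that the 4,800 women attending Down syndrome screening over about seven months (Objective 1) represent the stillbirth catchment. Then 4,800 × 12/7 = 8,229 a year. Multiplying by 0.5 and by 0.001 to 0.003 gives 4.1 to 12.3 cases. Five lies inside this range, so it is a credible accrual figure.

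**What five cases can show.** Exact (Clopper-Pearson) 95% intervals:

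- 0/5: upper limit 1 − 0.025^(1/5) = 52.2%
- 1/5: 0.5 to 71.6%

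Other intervals for 0/5 give somewhat lower upper limits: 43.4% (Wilson) and 45.1% (one-sided exact). For contrast, 0/500 has an exact upper limit of 0.7%, and 5/500 gives 0.3 to 2.3%.

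Chance of each result at the protocol's quoted rates, used only as illustrations:

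| True rate p | P(0 of 5) = (1−p)^5 | P(1 of 5) = 5p(1−p)^4 |
|---|---|---|
| 1% | 95.1% | 4.8% |
| 2.9% | 86.3% | 12.9% |
| 3.8% | 82.4% | 16.3% |
| 13.5% | 48.4% | 37.8% |

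**Would recruiting more secure the aim?** Take the catchment that 500 miscarriages in six months would need, with first- and second-trimester loss at 10% + 1%, uptake 50% and no private-care factor: 500 / 0.5 / 0.11 × 2 = 18,182 pregnancies a year. The stillbirth yield is 18,182 × 0.5 × (0.001 to 0.003) = 9.1 to 27.3. At those sizes:

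- 0/9 has an upper limit of 33.6%, and 1/9 is 11.1%.
- 0/27 has an upper limit of 12.8%, and 1/27 is 3.7%, still above 1% and 2.9%.
- Zero positives exclude 13.5% only from n = 26, since 1 − 0.025^(1/26) = 13.2% and 1 − 0.025^(1/25) = 13.7%.
- A 95% chance of at least one positive needs n = ln(0.05)/ln(1−p): 299 at 1%, 102 at 2.9%, 78 at 3.8%, 21 at 13.5%.

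The 70% private-care figure is ambiguous. If 70% stay in public care the yield is 13 to 39; if 70% leave it is 30 to 91. A lenient reading (450 miscarriages accepted as about 500, second-trimester cases over 12 months, stillbirth rate per surviving pregnancy) needs 450 / 0.5 / (0.10 × 0.5 + 0.01) = 15,000 pregnancies and gives 15,000 × 0.89 × 0.5 × (0.001 to 0.003) = 6.7 to 20.0. Across all readings the yield runs from about 7 to 91. Only the very top passes 78, and none reaches 102 or 299.

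**The case for a change.** The best argument for a change is that the protocol itself fixes the aim, the number and the summary, and never calls the stillbirth part exploratory. No later analysis plan can draw a usable rate from five women. Pooling all 505 losses does not rescue it, because stillbirths would then be 1% of the data. Limiting the rate aim to miscarriage would cost only words, and the apparent mismatch of catchments suggests that more stillbirths could be found.

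Part of this stands. The arithmetic is right, and the language of determining a rate is stronger than five cases can bear.

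The rest does not carry it to a change. The catchment argument rests on a population the protocol does not state and on three readings of one ambiguous percentage. The two targets need not share sites, and the lenient low end of 6.7 is close to 5. The quoted benchmark rates are swab positivity in asymptomatic women at delivery and an assumed seroconversion level. Neither is an expected rate in stillbirth, where several specimens are tested and infection may be over-represented. The feared misreading of 20% needs a comparison that the plan does not make, and with counts reported a reader will see one woman in five.

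**Conclusion.** No change is needed. Five is an expected one-year accrual of a rare event. It is plausible on the protocol's own figures, and no stated precision or power for stillbirth is missed. The limit is real (0 to 52% for 0/5, 0.5 to 72% for 1/5) but evident from the number itself, and any competent report will show the count, ideally with an exact interval and apart from miscarriage.

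Neither remedy improves the answer enough to justify itself. Widening recruitment may need new ethics approvals, and on the plainest reading it gives 9 to 27 cases, where zero positives still allow 34% or 13%. Removing stillbirth from the rate aim would relabel the same women, whose tissue already feeds Objective 5 if positive, and would drop a question without making any estimate more precise or less biased. The miscarriage rate, from 500 of 505 women (99%), is untouched.

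This conclusion assumes that stillbirths are reported as counts and that no claim of a stillbirth-specific effect is made from them, as the plan now stands. It would weaken if the available stillbirth catchment were shown to be near the top of the 7 to 91 range, which the protocol does not establish.
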